6.2.1.1 Pregnancy testing

For WOCBP, a serum pregnancy test will be performed at screening. Following a negative serum pregnancy result at screening, appropriate contraception must be commenced or continued and a further negative urine pregnancy test results will then be required at the baseline visit before the patient may receive the investigational product. Urine pregnancy tests will also be routinely repeated at study drug administration visits prior to study drug administration, at the last follow up visit day (Day 270) and additionally whenever 1 menstrual cycle is missed or when potential pregnancy is otherwise suspected. In the case of a positive pregnancy test or confirmed pregnancy, the patient will be discontinued from study drug, an EOT visit should be performed (Day 180), and a last follow-up visit 90 days after last dose should be scheduled (Day 270). Safety follow-up visit procedures (see [Section 5.4](#)) are specified in the Schedule of Assessments (see [Section 3.4](#)).

See [Section 6.2.2.7.1](#) for information on reporting of pregnancies as AEs/SAEs during the study.

6.2.1.2 Tuberculosis Screening

During the screening period, it must be determined and documented that a patient does not have evidence of active or latent or inadequately treated TB per the exclusion criteria ([Section 4.5](#)). The results of TB screening, which includes the QuantiFERON[®]-TB Gold In-Tube (QFT-G) test and a chest x-ray, conducted in the 3 months prior to screening or during the screening period must be documented in study records prior to randomization (Day 0).

6.2.1.2.1 Mycobacterium Tuberculosis Testing Using QuantiFERON Test⁴⁰

QuantiFERON[®]-TB Gold In-Tube (QFT-G) is an *in vitro* diagnostic test using a peptide cocktail simulating ESAT-6, CFP-10, and TB 7.7 proteins to stimulate cells in heparinized whole blood. Detection of INF γ performed by enzyme-linked immunosorbent assay (ELISA) is used to identify *in vitro* responses to these peptide antigens that are associated with Mycobacterium tuberculosis infection. QFT-G is an indirect test for M. tuberculosis infection (including disease) and is intended for use in conjunction with risk assessment, radiography and other medical and diagnostic evaluations.

Test results will be reported as positive, negative, or indeterminate. A negative QFT-G test result is required to meet the inclusion criterion. In the case of an indeterminate result, repeat tests should be permitted for the purpose of determining eligibility of patients to enroll in this study. If a repeat test is indeterminate again, the patient is a screen failure. The procedure for

using this test and interpreting the results will be described fully in the laboratory manual, which will be provided to investigators.

6.2.2 Adverse Events

6.2.2.1 Definitions

An AE is defined as any untoward medical occurrence experienced by a study patient, whether or not considered drug related by the principal investigator.

AEs are unfavorable changes in a general condition, subjective or objective signs or symptoms, worsening of pre-existing concomitant disease, and clinically significant abnormality in laboratory parameters observed in a patient in the course of a clinical study.

Non-serious SLE manifestations or abnormal laboratory results related to SLE disease activity would not be recorded as AEs unless they meet the definition for SAEs ([Section 6.2.2.5](#)).

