1.2.5 Potential Risks

Potential risks based on the mechanism of action of BOS161721 include infections, risks associated with the administration of any foreign protein or biologic agent, including injection site reaction, anaphylaxis, serious allergic reaction, and development of ADAs. ADAs could result in immune complex disease (with manifestations such as arthralgias, serum-sickness, and vasculitis), or altered BOS161721 levels or activity. Further details can be found in the current Investigator's Brochure (IB) for BOS161721, which contains comprehensive toxicology, preclinical and clinical information on BOS161721.

Two investigational drug products are considered to be in the same pharmacological class as BOS161721 based on interruption of signaling through the IL-21 signaling pathway. No potential risk generalizable across the class has been observed with these investigational products. Based on the clinical Phase 1 SAD study (BOS161721-01), AEs reported as related to the study drug, particularly infections (flu-like symptoms, etc.), were expected for the compound, and there were no clinically relevant changes in laboratory and ECG results or vital signs.

The majority of IgG elimination occurs via intracellular catabolism, following fluid-phase or receptor-mediated endocytosis. This type of endocytosis and elimination is a form of target-mediated disposition where the interaction of the drug and its pharmacological target (eg, a target receptor) serves as a significant contributor to the kinetics of antibody distribution and elimination. Renal elimination, which is a primary pathway of clearance of small-molecule drugs, is relatively unimportant for IgG, as its large size prevents efficient filtration through the glomerulus. Secretion into the bile is an important pathway of elimination of IgA antibodies, but

this route is not a significant contributor to the elimination of IgG antibodies. Thus, risk to renal and hepatic systems due to metabolism of BOS161721 is low.³³

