1.2.5.3 Immune Complex Disease

The potential risk of immune complex disease for BOS161721 is theoretical, based on the known risks associated with mAbs. The administration of a mAb can result in the formation of ADAs. Administration of the mAb in the presence of ADA may result in the formation of circulating antibody-antigen complexes potentially resulting in altered BOS161721 levels or activity or deposition of the complexes in microvasculature. Complement is frequently involved in the latter setting, and the breakdown products of complement attract polymorphonuclear leukocytes to the site of deposition where they can provoke local tissue damage through specific or nonspecific release of enzymes. Two of the more common end-organ targets are the blood vessels (vasculitis) and kidney (nephritis). These clinical manifestations represent immune complex disease or Type III hypersensitivity. Although BOS161721 is a humanized mAb,

ADAs may develop; however, the likelihood of occurrence of immune complex disease with BOS161721 is low. The findings of immune complex disease are typically reversible when mAb administration stops and the antibody-antigen complexes are cleared from the body.

Based on the Phase 1 SAD study (BOS161721-01), immune complex disease in subjects who received BOS161721 was not observed.

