3 STUDY PLAN

3.1 Study Design

This is a Phase 1b/2 combined, randomized, multicenter, double-blind, placebo-controlled trial to study the clinical efficacy, safety, and PK of SC doses of BOS161721 in adult patients with moderately to severely active SLE. After successfully completing a screening phase, eligible patients will be randomized to a specified dose of BOS161721 or placebo. The dosing schedule will be monthly.

The trial will consist of 2 double-blinded portions: MAD Phase 1b and POC Phase 2. Patients may receive a total of 7 SC monthly doses of study drug on Days 0, 30, 60, 90, 120, 150, and 180, followed by safety follow-up visits at Days 210, 240, and 270.

SLE disease activity assessment data will be centrally reviewed by medical monitor and sponsor to ensure the scores are clinically meaningful and compliant with specific definition. The scope of responsibility includes, but is not limited to, review and confirmation of “A” and “B” BILAG system organ disease, confirmation of clinical components of the SLEDAI-2K score at screening and during the study, and cross-validation of the instruments used in this study to assess the disease activity. Further details on the content and methods of data reports by the medical monitor and sponsor will be outlined in the Medical Data Review Plan along with the processes and procedures that will be followed.

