3.1.2.1 BOS161721 POC Dose Selection and Justification

The dose for the POC portion of the study is 120 mg administered SC monthly (a total of 7 doses). The rationale for the BOS161721-02 Phase 2 POC dose selection was based on cumulative safety, tolerability, immunogenicity, PK, and PD data available from an interim analysis (IA) performed during the MAD Phase 1b portion of the trial.

The data cut-off for this IA occurred on **CCI** and included all 6 patients and 7 doses from Cohort 1 (20 mg), 12 patients and 6 doses from Cohort 2 (60 mg), and 12 patients and 4 doses from Cohort 3 (120 mg).

The safety analysis focused on incidence and severity of all AEs, SAEs, and pre-determined adverse events of special interest (see [Section 6.2.2.6](#)). The DMC and designated unblinded Boston Pharmaceuticals team met on **CCI** and did not identify any untoward safety signals at any BOS161721 dose levels.

Because there were no safety, tolerability, or immunogenicity trends observed at the time of the IA, the Phase 2 POC dose selection was made based on available PK and PD data. pSTAT3 levels were assessed as the primary PD biomarker of IL-21R signaling levels. This is because IL-21R signaling, upon IL-21 binding, initially involves phosphorylation of JAK1/JAK3 which dissociate from the receptor complex, and phosphorylate STAT3 which translocates to the nucleus and drives IL-21-regulated gene expression. CCI

The 120 mg dose will be communicated to site investigators participating in the POC Phase 2 portion, and to Institutional Review Boards (IRBs) and the Independent Ethics Committee (IEC).

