4.4 Inclusion Criteria

Patients who meet the following criteria will be considered eligible to participate in this clinical study:

1. Men and women, ages 18 to 70 years, inclusive
2. Patients must be mentally capable of giving consent and there must be evidence of a personally signed and dated informed consent document indicating that the patient has been informed of all pertinent aspects of the study
3. Patients must have SLE as defined by meeting 4 of the Systemic Lupus International Collaborating Clinics (SLICC) classification criteria for SLE (with at least 1 clinical and 1

immunologic criterion or Lupus nephritis as the sole clinical criterion in the presence of ANA or anti-dsDNA antibodies), either sequentially or simultaneously

4. At screening, patients must have at least 1 of the following:
 - a. Elevated ANA \geq 1:80 via immunofluorescent assay at the central laboratory
 - b. Positive anti-dsDNA or anti-Smith (Sm) above the normal level as determined by the central laboratory
 - c. C3 or C4 levels below normal as determined by central lab
5. At screening, the SLE Disease Activity Index 2000 (SLEDAI-2K) must be \geq 6, including points from at least 1 of the following clinical components:
 - a. Arthritis, rash, myositis, mucosal ulcers, pleurisy, pericarditis, and vasculitis
 - i. Excluding parameters which require central laboratory results: hematuria, pyuria, urinary casts, proteinuria, positive anti-dsDNA, decreased complement, thrombocytopenia, and leukopenia
 - ii. Points from lupus headache and organic brain syndrome will also be excluded
6. On Day 0, the SLEDAI-2K must be \geq 6, including points from at least 1 of the following clinical components:
 - a. Arthritis, rash, myositis, mucosal ulcers, pleurisy, pericarditis, and vasculitis
 - i. Excluding parameters which require central laboratory results: hematuria, pyuria, urinary casts, proteinuria, positive anti-dsDNA, decreased complement, thrombocytopenia, and leukopenia
 - ii. Points from lupus headache and organic brain syndrome will also be excluded
7. Patients must have at least 1A or 2Bs from the following manifestations of SLE, as defined by the BILAG criteria as modified for use in this study, which must be confirmed by the central data reviewer:
 - a. BILAG A or B score in the mucocutaneous body system
 - b. BILAG A or B score in the musculoskeletal body system due to active polyarthritis defined as follows:

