6.2.2.6 Adverse Events of Special Interest

AEs of special interest in this study include the following:

1. Anaphylaxis and serious allergic reactions
2. Grades 2 to 5 injection site reaction, including erythema, pain, and induration (See [APPENDIX 6](#))
3. Drug Induced Liver Injury (DILI) assessed following Hy's Law
4. Malignancy (not including basal cell carcinoma or squamous cell carcinoma of skin)
5. Opportunistic infections such as disseminated histoplasmosis, cryptococcosis, disseminated herpes simplex, disseminated tuberculosis, *Aspergillus* sp., *Candida albicans*, *Coccidioides immitis*, *Cryptococcus neoformans*, *Cytomegalovirus*, *Histoplasma capsulatum*, *Isospora belli*, and *Polyomavirus JC polyomavirus*
6. Cryptosporidiasis

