8.2.5 Analysis of Safety

8.2.5.1 Safety Analysis

Safety analyses will be performed on the SS. AE data will be coded to system organ class and preferred term using MedDRA. The number and percentage of patients experiencing any treatment-emergent AE, overall, and by system organ class and preferred term, will be tabulated. Treatment-emergent AEs will also be summarized by severity and relationship.

Concomitant medications will be coded using the WHO Drug dictionary. Observed values and changes from baseline in vital signs, ECG readings, and hematology and clinical chemistry parameters will be summarized at each individual visit.

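### ADA samples from Days 180 and 270 are collected from everyone but assayed only after a positive Day 90, so seroconversion over the last 3 of 7 doses goes unmeasured; the AE rule for events that could be lupus or immune complex disease also needs a short clarification

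*Protocol*

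**What the plan says.** **ADA testing.** Section 6.2.8, Table 1 footnote k and Table 2 footnote l give the same rule. ADA is assayed in all patients up to Day 90. Later samples are drawn from all patients, but the laboratory analyses them only where Day 90 was positive. The footnotes put the same Day 90 condition on the neutralizing antibody assay, whereas the text of 6.2.8 extends that assay to any confirmed ADA positive after the first dose. Section 2.2 lists ADAs among the Phase 2 safety endpoints, and Section 2.1 makes immunogenicity part of the Phase 1b primary objective.

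**The named risk.** Section 1.2.5 states that "ADAs could result in immune complex disease (with manifestations such as arthralgias, serum-sickness, and vasculitis". Section 1.2.5.3 adds: "Two of the more common end-organ targets are the blood vessels (vasculitis) and kidney (nephritis". The same section calls the risk theoretical and of low likelihood, and says the findings usually reverse once dosing stops.

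**AE recording.** Section 6.2.2.1 says: "Non-serious SLE manifestations or abnormal laboratory results related to SLE disease activity would not be recorded as AEs unless they meet the definition for SAEs". No exception is made for suspected immune complex disease. The list in Section 6.2.2.6 that opens "AEs of special interest in this study include the following" has six entries, and immune complex disease is not one of them.

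**The concern.** ADA is the measurement that would connect a late immune-mediated event to the drug. The protocol draws the samples but, as written, leaves them unassayed in every patient who was negative on Day 90. A patient who was positive earlier but negative on Day 90 is also lost to later testing. An ADA incidence reported through Day 270 would then count late follow-up as negative when it was not tested.

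The AE wording adds a smaller difficulty. The signs of immune complex disease overlap with lupus, and investigators are blinded. Faced with a non-serious event that could be either, an investigator cannot tell from 6.2.2.1 whether to record it. If it is left out, the planned summary, "The number and percentage of patients experiencing any treatment-emergent AE, overall, and by system organ class and preferred term, will be tabulated", does not include it.

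**Working it through.** The protocol gives no figure on this point to reproduce. The check is a count from the schedule, an exposure calculation that bears on the ADA point only, and a comparison of text for the AE point.

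**1. Schedule (Table 2 and Section 3.1).**
- ADA samples: Days 0, 15, 30, 60, 90, 180, 270, which is 7. Conditional on Day 90: Days 180 and 270, which is 2 of 7.
- Doses: Days 0, 30, 60, 90, 120, 150, 180. Strictly after Day 90: Days 120, 150 and 180, which is 3 of 7. Counting the Day 90 dose itself gives 4 of 7.
- Follow-up after the last sample assayed in everyone: 270 − 90 = 180 of 270 days (67%).

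**2. Does exposure fall away after Day 90?** Assume linear first-order elimination, equal doses and immediate absorption. In units of one dose, with half-life h,

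L(t) = sum over dose days d < t of 2^(−(t − d)/h).

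For h = 80 days, L(90) = 2^(−90/80) + 2^(−60/80) + 2^(−30/80) = 0.4585 + 0.5946 + 0.7711 = 1.824. The other values follow in the same way.

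| Half-life (source) | Day 90 trough | Day 180 trough (ratio to Day 90) | Day 270 level (ratio to Day 90) |
|---|---|---|---|
| 80 d (1.2.2.3) | 1.824 | 2.661 (1.46) | 1.678 (0.92) |
| 87 d (1.2.2.3) | 1.896 | 2.821 (1.49) | 1.865 (0.98) |
| 44 d, interim (1.2.3) | 1.254 | 1.558 (1.24) | 0.620 (0.49) |

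Drug levels are higher on Day 180 than on Day 90 under every half-life in the protocol. With the final 80 to 87 day values they are still 92% to 98% of the Day 90 trough on Day 270. Declining exposure therefore gives no reason to stop testing Day 90 negatives.

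**3. Overlap between the named signs and lupus scoring.** Inclusion criterion 5 in Section 4.4 names these clinical SLEDAI-2K components: "Arthritis, rash, myositis, mucosal ulcers, pleurisy, pericarditis, and vasculitis". It also names hematuria, urinary casts and proteinuria among the laboratory items. Of the four signs in 1.2.5 and 1.2.5.3:
- vasculitis and nephritis map to scored items (2 of 4);
- arthralgia partly overlaps arthritis (1);
- serum sickness has no item (1).

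This shows that ambiguous events are possible. It says nothing about how often they occur.

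**The case against.** **Retrospective testing is possible.** The late samples exist, so a question raised later could be answered if they remain viable. That stands, and it is why the fix is cheap. But no such testing is planned, and assays chosen after the event would not give an incidence for the whole trial.

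**The interim review saw no immunogenicity trend.** Section 3.1.2.1 says so. At 120 mg, however, it covered 4 doses, and Phase 1b carries the same Day 90 condition. It says little about late conversion at the chosen dose.

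**The AE exemption is a common convention with other safeguards.** Most of this stands. An event recognised as immune complex disease is still an AE, and Section 6.2.2.2 allows individual symptoms to be reported when no diagnosis is established. Serious cases are SAEs. BILAG, SLEDAI-2K, urinalysis and protein/creatinine data keep the signs by arm, laboratory results are themselves a safety endpoint, and the DMC sees unblinded data. Disease activity data are also "centrally reviewed by medical monitor and sponsor to ensure the scores are clinically meaningful and compliant with specific definition". That stated purpose concerns scoring, but the scope is left open and the Medical Data Review Plan is not at hand.

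**Stronger readings that the documents do not support.** A reader might infer that 6.2.2.1 hides immune complex disease from the safety evaluation. It does not: it affects only non-serious events attributed to lupus, and their signs remain in the activity and laboratory data. A reader might also infer that the Phase 2 dose choice is undermined, because Section 3.1.2.1 says "The safety analysis focused on incidence and severity of all AEs, SAEs, and pre-determined adverse events of special interest". That decision also drew on immunogenicity, PK and PD data, and it is already made. Nor do the exposure figures measure lost AEs; they bear only on when ADA should be tested.

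**Conclusion.** The main point holds. Followed as written, the ADA rule leaves a listed safety endpoint unmeasured for new seroconversion over 3 of 7 doses and 180 of 270 days. ADA incidence through Day 270 can therefore be understated, and a late lupus-like event in a Day 90 negative has no planned ADA result to link it to drug. The size of the understatement cannot be derived, because the protocol gives no late conversion rate. The exposure ratios rest on the linear model above and on half-lives from healthy subjects; applying them to SLE patients is an assumption.

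The AE point is secondary. Section 6.2.2.1 is unclear for non-serious events that could be either lupus or immune complex disease, and a clarification would settle those. The protocol regards the risk as theoretical and of low likelihood. The change is worth making, but the primary efficacy analysis does not depend on it.

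**What to change.** 1. **Section 6.2.8, Table 1 footnote k, Table 2 footnote l.** Assay the collected Day 180 and Day 270 ADA samples in all dosed patients whatever the Day 90 result. At minimum, do so in every patient with suspected immune complex disease or with new vasculitis or nephritis. The minimum version supports interpretation of individual cases but does not repair the incidence estimate. Run the neutralizing antibody assay on any confirmed positive, and bring its footnotes into line. Since that assay is scheduled only on Days 90 and 180, say which sample serves a Day 270 positive.

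   Cost: up to two extra ADA assays per patient on samples already drawn, so at most 156 × 2 = 312 in Phase 2 at the planned enrolment and 30 × 2 = 60 in Phase 1b, plus neutralizing antibody tests on positives.

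2. **Sections 6.2.2.1 and 6.2.2.6.** State that investigator-suspected immune complex disease (serum sickness, or new vasculitis or nephritis not typical of the patient's prior lupus) is recorded as an AE and AESI even where lupus is a possible explanation. Leave isolated arthralgia and worsening of existing proteinuria out of the expedited route.

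   Cost: one sentence in each section, and some records with 24-hour reporting that prove to be lupus. This does not reach events the investigator simply attributes to lupus; those stay visible only in the BILAG, SLEDAI-2K and laboratory data.

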6.2.2.2 Recording of Adverse Events

AEs should be collected and recorded for each patient from the date of the first dose of study drug until the end of their participation in the study, including the safety follow up period.

AEs may be volunteered spontaneously by the study patient, or discovered by the study staff during physical examinations or by asking an open, nonleading question such as ‘How have you been feeling since you were last asked?’ All AEs and any required remedial action will be recorded on the Adverse Events eCRF and Safety Adverse Event Form. The details of the AE, date of AE onset, date of AE outcome, and action taken for the AE will be documented together with the principal investigator’s assessment of the seriousness of the AE and causal relationship to the study drug and/or the study procedure.

All AEs should be recorded individually, using diagnostic terms where possible. If the diagnosis is not established, individual symptoms may be reported. The AEs will subsequently be coded using the Medical Dictionary for Regulatory Activities (MedDRA).

6.2.2.3 Severity of Adverse Events

Each AE will be assessed by the principal investigator according to the National Cancer Institute Common Terminology Criteria for Adverse Events (NCI CTCAE), version 4.03 criteria.⁴¹ When changes in the severity (grade) of an AE occur more frequently than once a day, the maximum severity for the event should be noted for that day. Any change in severity of signs and symptoms over a number of days will be captured by recording a new AE, with the amended severity grade and the date (and time, if known) of the change.

